10 STUDY PROCEDURES

10.1 INDEPENDENT EFFICACY AND SAFETY ASSESSORS

A dual assessor approach will be required during this study in order to maintain the blind during the double-blind treatment period with sarilumab, placebo, and prednisone. The precise definitions of the efficacy and safety assessors' roles and responsibilities are specified in the Dual Assessor Guidance Document supplied to sites. An overview of those definitions is provided below.

Efficacy Assessor

The Efficacy Assessor will be responsible for completing the overall evaluation and management of GCA disease activity including the following:

- Assessment of clinical signs and symptoms of GCA (without access to ESR and any central laboratory data including CRP).
- Assessment of adherence to the protocol defined prednisone taper regimen.
- Management of rescue medication which is led by Investigator per protocol.

The Efficacy Assessor should not have access to central laboratory results obtained per protocol. If knowledge of the ESR is absolutely required in making a medical decision related to disease activity, the Efficacy Assessor may request the last available value obtained per protocol from the Safety Assessor or obtain a local laboratory value for ESR. Otherwise it is strongly recommended for the Efficacy Assessor not to have access to any laboratory data. Additionally, if necessary for the management of any safety concern for a particular patient that cannot wait to be addressed by the Safety Assessor, the Efficacy Assessor may arrange for local laboratory assessments to be performed and will have access to the results of these assessments.

To ensure consistency of assessments, it is encouraged that efficacy evaluations throughout the study be conducted by the same Efficacy Assessor for all study visits for a given patient, whenever possible.

It is mandatory that assessments by the Efficacy Assessor be completed before assessments by the Safety Assessor.

The Efficacy Assessor may permanently discontinue oral IMP (prednisone as per taper regimen) and initiate rescue therapy in order to properly manage disease activity, if necessary. In such a scenario, the SC IMP (sarilumab or matching placebo) may continue per protocol unless nonbiological immunosuppressive drugs are used and a safety concern is raised by the Safety Assessor.

Safety Assessor

The Safety Assessor will be responsible for assessing and managing any safety concerns of the patient during the course of the study. The specific responsibilities include:

- Eliciting and recording of any clinical and/or laboratory AEs.
- Management of any clinical and/or laboratory AEs.
- Review of all laboratory data (except CRP after baseline).
- Perform the assessments related to GTI.

The Safety Assessor may temporarily (or permanently) discontinue IMP (SC and/or oral) during the management of an AE and only the Safety Assessor may reinitiate the IMP upon his/her discretion. If the IMP is permanently discontinued, both Efficacy and Safety Assessors should be informed in order to make subsequent medical management decisions.

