STUDY DESIGN	
This is a multicenter, randomized, double-blind, placebo-controlled 52-week study with a 24-week post-treatment follow up phase, evaluating the efficacy and safety of sarilumab in patients with GCA.
 
Patients with GCA (new onset or refractory [eg, disease relapse] GCA defined as below) will be randomized to 4 parallel treatment groups with sarilumab 200 mg every 2 weeks (q2w), 150 mg q2w, or placebo q2w plus 26 week prednisone taper, or placebo with standardized prednisone taper of 52 weeks at a ratio of 2:1:1:2 as described below. Randomization will be stratified by the starting dose of prednisone at baseline (<30 mg/day or ≥30 mg/day).
 
• Treatment Group A: sarilumab 200 mg q2w with a 26 week taper of CS.• Treatment Group B: sarilumab 150 mg q2w with a 26 week taper of CS.• Treatment Group C: sarilumab matching placebo q2w with a 26 week taper of CS.• Treatment Group D: sarilumab matching placebo q2w with a 52 week taper of CS. 
Patients will be dosed with prednisone between 20 to 60 mg/day at the time of randomization (baseline) and initiate taper according to the protocol defined schedule. Patients will have up to 7 weeks to taper down to prednisone dose of 20 mg/day following randomization. If, for example, the patient is randomized on 20 mg prednisone per day, the patient will start the blinded, standardized prednisone taper 1-week after randomization. For other patients randomized on higher prednisone doses, upon reaching prednisone of 20 mg/day, patients will be initiated on a blinded, standardized taper of prednisone of up to 26 weeks or up to 52 weeks from time of randomization.
 
The protocol will aim to enroll at least 30% of new onset patients, therefore, the Sponsor will reserve the possibility to cap enrolment of refractory patients to ≤70% of total patients randomized.
 
For the management of predefined neutropenia, thrombocytopenia and alanine aminotransferase increases, study drug(sarilumab or matching placebo) must be temporarily withheld, and may be reduced to sarilumab 150 mg q2w (for patients randomized to the 200 mg q2w arm only) based on Investigator judgment. The request for dose reduction will be managed via IRT and the sarilumab dose prior to and following the dose reduction will remain blinded to site and Sponsor (for patients in the sarilumab 150 mg or sarilumab matching placebo groups, there will be only a sham dose reduction to maintain the blind).
 
During the course of study, for patients in need of rescue therapy as per Investigator judgment, CS should be the agent of first choice. Patients may continue subcutaneous (SC) administration of sarilumab or matching placebo only if CS is used as rescue therapy. If the patients remain symptomatic despite CS rescue therapy, then other treatment options including nonbiological immunosuppressive drugs may be used and the patient must be discontinued from the study treatment and considered a nonresponder.
 
All patients who prematurely and permanently discontinue study medication will be asked to return to the site for study assessments as per protocol until end of study (EOS) evaluation.

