During the course of study, for patients in need of rescue therapy as per Investigator judgment, CS should be the agent of first choice. Patients may continue SC administration of sarilumab or matching placebo only if CS is used as rescue therapy. If the patients remain symptomatic despite CS rescue therapy, then other treatment options including nonbiological immunosuppressive

drugs may be used and the patient must be discontinued from the study treatment and considered a nonresponder.

If the patient or Investigator decides to discontinue the administration of blinded sarilumab injections, then the patient will be asked to return to the site for study assessments as per protocol until end of study (EOS) evaluation, unless the patient cannot or does not wish to continue the assessments, in which case an early withdrawal visit and safety follow up should be performed. It is recommended that patients complete Visit 13, if possible.

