8.2 NONINVESTIGATIONAL MEDICINAL PRODUCT(S)

Rescue therapy

At each study visit, an assessment of the patient's GCA disease status should be made. If the patient has no evidence for disease flare and is able to follow the per protocol prednisone taper schedule, the patient will continue with the per protocol prednisone taper of the study as per [Appendix B](#) for up to 52 weeks. If the patient experiences a disease flare or cannot adhere to the prednisone tapering schedule, then the patient must stop the per protocol prednisone taper and instead may receive rescue therapy, such as CSs, as per Investigator's clinical judgment. The patient should continue in the double-blind period of the study for the full 52 weeks and should continue to receive blinded SC injections unless contraindicated by safety concerns and complete the remainder of the study assessments.

Once the patients are on rescue therapy at the discretion of Investigators, it is not allowed for them to return to per protocol prednisone taper regimen.

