8.8 LIST OF FORBIDDEN AND PERMITTED CONCOMITANT MEDICATIONS

A concomitant medication is any treatment received by the patient concomitantly to any IMP(s).

The use of any biologics for treatment of GCA during the study is not permitted throughout the study treatment and until 6 weeks following the last SC IMP (sarilumab or matching placebo) administration unless otherwise indicated. If any of these treatments is used, the patient should be discontinued from IMP treatment but the patient will continue to be monitored for safety.

Administration of any live (attenuated) vaccine is contraindicated until 3 months following the last IMP (sarilumab or matching placebo) administration. Treatment with non-biological immunosuppressive drugs (such as alkylating agents, hydroxychloroquine, CsA, MMF, AZA, etc) is not permitted during the course of the study, unless used for the purpose of rescue therapy.

During the course of study, for patients in need of rescue therapy as per Investigator judgment, CS should be the agent of first choice. Patients may continue SC administration of sarilumab or matching placebo only if CS is used as rescue therapy. If the patients remain symptomatic despite CS rescue therapy, then other treatment options including nonbiological immunosuppressive drugs may be used and the patient must be discontinued from the study treatment and considered a nonresponder.

Methotrexate not exceeding 25 mg per week is permitted if the dose has been stable for at least 3 months prior to baseline. The dose should also remain stable (may be reduced or discontinued if for safety reasons, if necessary), but should not be initiated or increased throughout the study treatment duration and until 6 weeks following the last SC IMP (sarilumab or matching placebo) administration.

Treatment with any IMP other than sarilumab and prednisone defined by protocol is not permitted.

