10.4.3 List of criteria for permanent treatment discontinuation

The patients may withdraw from treatment with the IMP if they decide to do so, at any time and irrespective of the reason, or this may be the Investigator's decision. All efforts should be made to document the reason(s) for treatment discontinuation and this should be documented in the eCRF.

Investigational medicinal products will be permanently discontinued in case of the following events (refer to [Section 10.7](#) for details):

- Opportunistic infections (as assessed by the Investigator) including, but not limited to, active TB.
 - The initial diagnosis of TB may be made either on symptoms or on a chest radiograph suggestive of active TB. Patients should be referred to appropriate medical specialists and whenever possible, culture confirmation of disease should be obtained and recorded in the eCRF.
 - Culture positive for nonTB mycobacteria.
- The patient is at risk through close contact with a person with active TB and the patient refuses to undergo TB evaluation.
- Symptoms of systemic hypersensitivity or anaphylactic reactions.
- Severe neurologic disease such as demyelinating disease or PML.
- Significant laboratory abnormalities:
 - ALT >5 x ULN or ALT >3 x ULN with concomitant total bilirubin >2 x ULN (unless patient with documented Gilbert's Syndrome).
 - neutrophil count <500/mm³, or neutrophil count <1000/mm³ with evidence of infection.
 - platelet count <50 000/mm³, or platelet count <100 000/mm³ with evidence of bleeding.
- Acute renal failure (refer [Section 10.7.8](#)).
- Pregnancy in female participant.
- Use of any biologic DMARDs other than IMP.
- Any AEs, per Investigator's judgment, that may jeopardize the patient's safety.

Any abnormal laboratory value will be immediately rechecked for confirmation before making a decision of permanent discontinuation of the IMP for the concerned patient.

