During the course of study, for patients in need of rescue therapy as per Investigator judgment, CS should be the agent of first choice. Patients may continue SC administration of sarilumab or matching placebo only if CS is used as the rescue therapy. If the patients remain symptomatic despite CS rescue therapy, then other treatment options including nonbiological immunosuppressive drugs may be used and the patient must be discontinued from the study treatment and considered a non-responder.

If the patient or Investigator decides to discontinue the administration of blinded sarilumab injections, then the patient will be asked to return to the site for study assessments as per protocol until end of study (EOS) evaluation, unless the patient cannot or does not wish to continue the assessments, in which case an early withdrawal visit and safety follow up should be performed. It is recommended that patients complete Visit 13, if possible.

Total duration of study participation for each patient is up to 82 weeks:

- Up to 6 weeks screening period.
- 52-week treatment period (sarilumab or placebo, double-blind phase).
- 24-week post treatment follow-up period.

The last patient last visit will occur when the last patient has completed the 24-week follow up period (EOS). The end of the clinical trial is defined as the last patient's last visit.

Study discontinuation plan

As mentioned in [Section 1](#), due to the protracted recruitment timeline and internal portfolio reprioritization, Sanofi has decided to terminate the EFC15068 study in July 2020. For patients who were already enrolled with ongoing treatment in the study, investigators were instructed to discontinue the study drugs and transition these patients into post-treatment follow-up period for safety assessments. The study discontinuation plan is as follows:

- All randomized patients should stop by 12 weeks from the date of announcement to the sites and should be scheduled for the end of study treatment visit at their earliest

convenience and no later than *October 13, 2020*, which would ensure sufficient time for patients to identify alternative therapy as needed.

- All patients will have a follow-up (EOS) visit that is 6 weeks after treatment cessation and no later than *November 24, 2020*.

Thus, the last patient last visit will occur when the last patient has completed the 6-week follow-up period (EOS). The end of the clinical trial is defined as the last patient's last visit.

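### Protocol 10.1, read literally, lets SC sarilumab or placebo continue after rescue with a nonbiological immunosuppressant unless a safety concern is also raised; the protocol's own stop rule forbids this (minor)

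*Protocol*

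**What the plan says.** Protocol 10.1 sets out what the Efficacy Assessor, who manages rescue, may do. That assessor may stop the oral prednisone taper for good and start rescue, in which case "the SC IMP (sarilumab or matching placebo) may continue per protocol unless nonbiological immunosuppressive drugs are used and a safety concern is raised". The concern meant there is one coming from the Safety Assessor.

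The stop rule is stated in Protocol 8.8: "Patients may continue SC administration of sarilumab or matching placebo only if CS is used as rescue therapy". For patients still symptomatic despite corticosteroid (CS) rescue, it adds that "nonbiological immunosuppressive drugs may be used and the patient must be discontinued from the study treatment and considered a nonresponder". The same rule appears in:

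- the Clinical Trial Summary: "the patient must be discontinued from the study treatment and considered a nonresponder"
- Protocol 6.1: "drugs may be used and the patient must be discontinued from the study treatment and considered a nonresponder"
- SAP 1.1: "the patient must be discontinued from the study treatment and considered a non-responder"

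Two other sections deal with stopping injections and do not state the rule. Protocol 8.2, on rescue therapy, says the patient "should continue to receive blinded SC injections unless contraindicated by safety concerns". The list of mandatory stopping criteria in Protocol 10.4.3 includes "Use of any biologic DMARDs other than IMP", but has no entry for nonbiological immunosuppressants.

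**The concern.** Four statements make discontinuation mandatory once a nonbiological immunosuppressant is used as rescue, and none of them depends on a safety concern. Section 10.1 adds that dependence. It is also the text addressed to the person choosing the rescue drug, and it requires that person's assessments to be completed before the Safety Assessor's. A site could start the drug, have no safety concern on record, and read 10.1 as permission to keep injecting. Checking 8.2 and 10.4.3 would not correct that reading.

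What is at stake is mainly patient safety. Protocol 4.1 names serious infection and neutropenia among the identified risks of sarilumab, and exclusion E 06 keeps out patients who took several of these agents within 4 weeks of baseline. Different site practice would also change SC exposure and the count of treatment discontinuations.

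Stable methotrexate up to 25 mg per week is permitted by 8.8 and is not part of this point.

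**Working it through.** **The two rules side by side.** Let A be a nonbiological immunosuppressant used as rescue, and B a safety concern raised by the Safety Assessor. Section 10.1 stops SC dosing if A and B. The stop rule (Summary, 6.1, 8.8, SAP 1.1) stops it if A.

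| A | B | 10.1, literal | Stop rule |
|---|---|---|---|
| no | no | may continue | may continue |
| yes | yes | stop | stop |
| yes | no | may continue | **must stop** |
| no | yes | may continue | silent; 8.2 and the Safety Assessor's powers in 10.1 allow stopping |

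The direct conflict is the third row. Replacing *and* by *or* turns 10.1 into stop if A or B. That removes the conflict and also fits the fourth row.

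**Primary endpoint.** Under 8.8 the immunosuppressant follows failed CS rescue. Protocol 11.4.2.1 already counts open-label prednisone rescue as nonresponse. In SAP 2.1.3.1, rescue from Week 12 on fails taper adherence, and CS rescue for active GCA before Week 12 fails remission by Week 12. Responder status therefore does not turn on whether injections continue.

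**Most further doses one patient could receive.** Inputs: dosing every 2 weeks from Week 0, last dose at Week 50 (flow chart, footnote c), and visit-day doses given after clinic procedures (Protocol 8.1.1). If the drug is started at Week w before that day's dose:

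- further doses = (50 − w)/2 + 1
- shift of the last dose in days = 7 × (50 − (w − 2))

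| Start | Further doses | Shift of last dose |
|---|---|---|
| Week 12 | 38/2 + 1 = 20 | 7 × 40 = 280 days |
| Week 24 | 26/2 + 1 = 14 | 7 × 28 = 196 days |
| Week 40 | 10/2 + 1 = 6 | 7 × 12 = 84 days |

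Started just after that day's dose, each row loses one dose and 14 days: 19 doses and 266 days, 13 and 182, 5 and 70.

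Lower end: SAP 1.3 says all 83 patients had the opportunity for at least 24 weeks. Assume a last dose at Week 22, by analogy with Week 50 of 52. A Week 12 start then allows (22 − 12)/2 + 1 = 6 further doses, a shift of 7 × (22 − 10) = 84 days. Starts at Week 24 or 40 allow none.

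**Who could reach Week 50.** That dose falls 50 × 7 = 350 days after randomization. SAP 1.1 sets 13 October 2020 as the latest end-of-treatment visit. Counting back 350 days gives 29 October 2019. The Week 52 Analysis set (SAP 2.3.1; 36 of 83 patients) requires randomization before 16 October 2019, so a patient randomized from 16 to about 29 October 2019 lies outside that set but could still reach the Week 50 dose. This assumes first dosing on the day of randomization and no required gap between the last dose and an early end-of-treatment visit; the documents state no such gap. With a two-week gap the cut-off would be 29 − 14 = 15 October 2019, the last day inside the set.

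**The case against.** The strongest reply is that the literal reading is the least plausible one. Taken strictly, 10.1 would also let injections continue after CS rescue when a safety concern has been raised, against 8.2 and against the Safety Assessor's own power to stop treatment. Two separate exceptions were surely intended. This stands as to intent, and it is why the remedy is a single word. It does not change what the sentence says.

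Second, 10.1 is permissive and qualified by a reference to the protocol, while the stop rule is mandatory and stated four times. That helps, but the sentence goes on to give its own, narrower exception, so the reader is not clearly sent back to 8.8.

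Third, 10.1 is an overview of a Dual Assessor Guidance Document supplied to sites. That document is not part of the protocol or SAP and may have been clear. Site handling is therefore unknown, but a document that cannot be read cannot be assumed to cure protocol text.

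Fourth, Protocol 4 describes sarilumab given with background DMARDs in rheumatoid arthritis, and 8.8 allows stable methotrexate, so combined use is not ruled out in principle. This is fair, but a newly started agent after failed CS rescue is a different situation, and the stop rule covers it expressly.

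Fifth, SAP 2.2 already tabulates critical or major deviations and SAP 2.4.2 summarizes concomitant medications. These cover part of the need. Neither names this case nor lists the doses given.

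**Conclusion.** The inconsistency is real and confined to one case. The label is wrong as written, minor. Confidence is high for the wording and low for any practical effect. The dose counts are hypothetical per-patient maxima; the documents give no evidence that a case occurred.

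A reader might infer more in four directions, none of which the documents support:

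- **Bias in the primary endpoint.** Rescue already makes the patient a nonresponder. An effect on the descriptive CRP component would arise only if permanent withdrawal from study treatment in SAP 2.1.3.1 means SC injections alone, which the SAP does not settle.
- **A distorted adverse-event window.** SAP 2.1.4 ends the treatment-emergent period 60 days after the last SC dose. A window that follows the actual last dose is working as designed.
- **Full bounds limited to the 36 patients in the Week 52 Analysis set.** That set is defined by reaching Week 52, whereas the bounds need only the Week 50 dose.
- **A deliberate second rule in 8.2 and 10.4.3.** Those sections omit the stop rule but do not contradict it.

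**What to change.** In Protocol 10.1, change the *and* before the safety-concern clause to *or*, so that either condition stops SC dosing and 8.8 governs. Adding the item to 10.4.3 and a cross-reference from 8.2 to 8.8 would be optional tidying.

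Because all treatment was to end by 13 October 2020, the useful step now is in the SAP. Add a listing of every SC dose given after a nonbiological immunosuppressant was started as rescue, excluding permitted stable methotrexate, with dates and number of doses by patient and group. Classify each case as a deviation from 8.8, noting that 10.1 could have been read as allowing it.

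The cost is one word and one listing from concomitant-medication and SC dosing records already collected. If there are no cases, one sentence in the study report closes the point.

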10.2 VISIT SCHEDULE

It is preferred that all study visits that require fasting blood samples to take place in the morning. The study visits occur on the planned dates (relative to randomization date), as scheduled. The visit schedule should be adhered to within the ± 3 day visit window. In general, PRO assessments should be completed at the study site as part of the visit (per study flow chart [Section 1.2](#)) but prior to any meaningful communication with a health care professional or any other study procedures, unless noted otherwise in the suggested order of the study procedures for each individual visit described below:

- Consent
- Eligibility
- Randomization
- PRO questionnaires
- GCA assessments
- Other clinical assessments and AE reporting
- Blood sampling
- IRT call to obtain resupply treatment
- Dose administration

